7.7 EXTENT OF EXPOSURE

Exposure will be presented as total days on treatment and total study medication intake assessed by actual treatment received. For example, a Placebo patient that switches to BI 730357 100 mg at Week 12 should have 12 weeks of exposure under the Placebo column and their number of days on BI 730357 100 mg under BI 730357 100 mg column.

7.8 SAFETY ANALYSIS

All safety analyses will be performed on the treated set (TS). Analysis will be performed as defined in Section 7.3.4 of the CTP.

7.8.1 Adverse Events

The analyses of adverse events will be descriptive in nature. All analyses of AEs will be based on the number of patients with AEs (not the number of AEs).

Unless otherwise specified, the analyses of AEs will be descriptive in nature. All analyses of AEs will be based on the number of subjects with AEs and NOT on the number of AEs.

The analysis of AEs will be based on the concept of treatment emergent AEs. That means that all AEs occurring between first drug intake till 7 days after last drug intake will be assigned to the received treatment. All AEs occurring before first drug intake will be assigned to 'screening' and all AEs occurring after last drug intake + 7 days will be assigned to 'follow-up' (for listings only). For details on the treatment definition, see [Section 6.1](#).

According to ICH E3 [\(5\)](#), in addition to Deaths and serious adverse events, 'other significant' AEs need to be listed in the clinical trial report. These will be any non-serious adverse event that led to an action taken with study drug (e.g. discontinuation or dose reduced or interrupted). An overall summary of adverse events will be presented.

The frequency of subjects with AEs will be summarised by treatment, primary system organ class and PT using the version of MedDRA at the database lock. Separate tables will be provided for subjects with SAEs, AEs leading to treatment discontinuation and related AEs.

The system organ classes will be sorted by default by decreasing frequency and PTs will be sorted by decreasing frequency within SOC.

For further details on summarization of AE data, please refer to the guideline 'Handling and summarization of adverse event data for clinical trial reports and integrated summaries' [\(4\)](#).

The severity of AEs will be summarised by the maximum intensity of the events each patient had (as indicated by the recorded RCTC version 2 grade). This will show the number and percent of patients who had at most mild, moderate, severe, and life threatening events. Severe adverse event is defined as an AE with RCTC grade equals to 3 (severe) or 4 (life threatening).

Groupings of adverse events and adverse events of special interest (AESI)

The AESI have been defined in the protocol.

Other user-defined special adverse event grouped term for BI 730357 specified in the following [Table 7.8.1:1](#).

Table 7.8.1: 1 User Defined Adverse Event Group Terms

N	Term	Definition #
1	SMQ Drug Related Hepatic Disorders	SMQ Drug related hepatic disorders – comprehensive search (20000006)
2	SMQ Opportunistic infections	MedDRA SMQ Opportunistic Infections (narrow)
3	Tuberculosis related terms	BIcMQ “Tuberculosis related terms” BIcMQ (30000107)(broad)
4	Severe infections	SOC “Infections and infestations” with eCRF severity grade >= Rheumatology Common Toxicity Criteria (RCTC) Grade 3
5	Gastritis related terms	
 BIcMQ Gastritis (broad) [32008061]

This column indicates whether the Term(s) provided in the second column are MedDRA preferred terms (PT), Standardised MedDRA Queries (SMQ) or BI customised MedDRA Queries (BIcMQ).

In addition, adjudicated MACE (provided by [REDACTED] will be summarized by indication, treatment, primary system organ class and preferred term.

The user defined AE categories will be updated accordingly with Safety SAP updates.

The following periods will be defined for assessing adverse events for patients from Part 1 of the 1407-0030 trial.:

- First 12 weeks of treatment
- Second treatment period

For patients from Part 1 of the 1407-0030 trial, AEs with onset date on day of week 12 visit, the AE onset time will be compared with first drug administration time of the dose dispensed at the Week 12 visit to determine AE period. The treatment label for second period will be a combination of actual treatment in first 12 weeks of treatment and second period treatment.

Additionally an analysis including patients from both parts of the 1407-0030 trial will be performed in which adverse events are classified under the dose the patient was receiving at the onset of the TEAE.

AE summaries

An overall summary of adverse events will be presented. The frequency of patients with adverse events will be summarized by treatment, primary system organ class and preferred term according to MedDRA. Separate tables will be provided for patients with:

- Drug-related AEs
- AESIs

- AEs leading to discontinuation
- Serious AEs
- Other significant AEs
- AE by worst RCTC intensity
- Investigator defined drug-related serious AEs
- User defined AE categories

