1.4 BENEFIT - RISK ASSESSMENT

Study participants are exposed to the risks of the study procedures and the risks related to the exposure to the trial medication.

Procedure-related risks

Blood sampling by venipuncture or through an indwelling venous catheter may be accompanied by mild bruising and also, in rare cases, by transient inflammation of the wall of the vein. In addition, in rare cases a nerve might be injured while inserting the venous catheter, potentially resulting in paresthesia, reduced sensibility, and/or pain for an indefinite period.

No health-related risk is expected from the total planned blood withdrawal over approximately 6 years.

Drug-related risks and safety measures

As the nature of the target and the mechanism of action of BI 730357 are well understood, comparable compounds have been tested by other companies before, and the animal models

Page 22 of 84

are believed to be predictive for the effects in humans, BI 730357 is not seen as a high risk compound.

The pharmacological effects of BI 730357 are dose dependent, and no evidence for prolonged or irreversible effects has been observed. Evaluation of BI 730357 dose levels selected for administration in this trial is supported by pre-clinical, as well as clinical safety data from Trial 1407.1 and 1407-0002 (see Section 1.2).

Dose reassignments planned in this trial (refer to Section 3.1) will be contingent on an independent external Data Monitoring Committee (DMC) evaluation of all available data from Phase II Trial 1407-0030 regarding the safety of the dose levels proposed (refer to Section 8.7).

Since preclinical data indicate that BI 730357 has phototoxicity potential, patients in this trial will be advised to apply protection measures as described in Section 4.2.2.2. Solarium radiation, or treatment with ultraviolet light (e.g., PUVA) or use of medication with known phototoxicity potential (e.g., doxycycline) is prohibited during this clinical trial until the end of the follow-up period.

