BI 730357 is confirmed as a sensitive cytochrome P450 (CYP) 3A substrate, based on clinical drug-drug interaction (DDI) evaluation with itraconazole, a CYP3A inhibitor, in trial 1407-0014. Drugs or foods that are known CYP3A inhibitors or strong or moderate CYP3A inducers should not be co-administered in clinical trials with BI 730357. Based on in vitro data, BI 730357 could potentially induce CYPs 1A2, 2B6, 2C8, 2C9, or 2C19 in human. Sensitive substrates of CYPs 1A2, 2B6, 2C8, 2C9, or 2C19 for which a reduction in exposure could present a potential patient risk should not be given together with BI 730357. Additionally, based on in vitro data, BI 730357 may inhibit a number of transporters in human; based on the magnitudes of the in vitro inhibition, it is recommended that substrates of P-gp, BCRP, OATP1B1, OATP1B3, OAT3, OCT2, MATE1, and MATE2-K for which an increase in exposure could present a potential patient risk should not be given together with BI 730357.

As with other immune-targeted therapies, impaired host defense is a theoretical target-related toxicity, potentially resulting in increased risk of infection and/or malignancy.

No evidence of an increased risk of lymphoma development or

changes preceding lymphoma development has arisen based on the BI 730357 toxicology studies in rat and dogs up to 26- and 39-week duration, respectively. AEs and SAEs consistent with malignancy, and specifically those representing lymphoma, are to be evaluated throughout the BI 730357 clinical development program. Thus far, no clinical signal regarding malignancy has been identified in BI 730357 clinical trials.

Page 23 of 84

As with all drugs, the potential for hypersensitivity and allergic reactions has to be taken into consideration when BI 730357 is administered.

Although rare, a potential for drug-induced liver injury (DILI) is under constant surveillance by sponsors and regulators. Therefore, this trial requires timely detection, evaluation, and follow-up of laboratory alterations in selected liver laboratory parameters to ensure patients' safety, see also Section 5.2.6, adverse events of special interest.

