4.2.2 Restrictions

4.2.2.1 Restrictions regarding concomitant treatment

The medications, classes of medications, and foods listed in Table 4.2.2.1: 1 must not be taken for the time periods as specified. Classes of antipsoriatic medications listed in Table 4.2.2.1: 1 are likewise restricted, however may be permitted as rescue treatment, at the Investigator's discretion, if a patient experiences an intolerable increase of PsO during the course of the trial and the patient is undergoing early treatment and trial termination. In such cases, the Investigator must notify the BI CML and document the details of the drug used and reason in the eCRF. A comprehensive list of restricted medications can be found in the ISF.

Page 39 of 84

Table 4.2.2.1: 1 Restricted antipsoriatic medications, concomitant treatments and food

Medication or class of medications	Specified restriction time	
Drugs with known phototoxic or photoallergic potential (e.g., tetracyclines, fluorchinolones)	One week prior to randomisation in preceding study until EOO in this study	
Drugs or foods (e.g., seville oranges, grapefruit, paw paw and their products) which are known inhibitors or moderate or strong inducers of CYP3A, or are sensitive substrates of CYP1A2 CYP2B6, or CYP2C8, CYP2C9, or CYP2C19.	One week prior to randomisation in preceding study until EOO in this study	
Drugs with narrow therapeutic windows which are substrates of P-gp, BCRP, OATP1B1, OATP1B3, OAT3, OCT2, MATE1, and MATE2-K	One week prior to randomisation in preceding study through EOO in this study	
Investigational device or product (other than antipsoriatic drugs)	30 days prior to randomisationin preceding study through EOO in this study	
Any drug known to interfere with or to aggravate PsO including but not limited to lithium and interferons	4 weeks prior to randomisation in preceding study through EOO in this study	
BCG (Bacillus Calmette-Guérin) vaccine	1 year prior to randomisation in preceding study through 1 year after last administration of study drug in this study	
Investigational antipsoriatic drugs	12 weeks prior to randomisation in preceding study through EOO in this study	
Systemic anti-psoriatic medications or phototherapy	12 weeks prior to randomisation in preceding through EOO in this study	

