4.2.2.2 Restrictions on diet and life style

The participants should take the medication after at least 6 hours fasting and should not eat for 30 minutes after drug administration.

Foods which are known strong or moderate inhibitors of CYP 3A (e.g., seville oranges, grapefruit, paw paw and their products) should be avoided during the study participation.

Moisturizers/emollients containing retinoids and the use of tanning beds are not allowed during the study.

Throughout their participation in the study, patients should avoid prolonged exposure to sunlight and artificial UV-light. When exposed to direct sunlight study participants should protect skin areas not covered by clothes by using sun-protection creams and lip balms with sun protection factor 30 or higher with protection against UV-A and UV-B. Patients should wear sunglasses when exposed to direct sun or other sources of UV-light. These protection measures must be applied until the end of the follow-up periods.

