7.4 PRIMARY ENDPOINT(S)

7.4.1 Primary analysis of the primary endpoint(s)

The primary endpoint is the occurrence of treatment emergent adverse events (TEAEs) up to Week 288. The primary analysis will be based on the exposure adjusted rate of patients reporting a treatment emergent adverse event (TEAE) up to Week 288.

Exposure-adjusted adverse event incidence rates will be calculated using the following approach:

- The incidence rate (per 100 subject years) of a selected adverse event (also known as the incidence density rate or person-time incidence rate) is defined as the number of subjects experiencing the adverse event per treatment group during the time at risk divided by the total time of subjects at risk in that treatment group to contribute an event to the analysis multiplied by 100 (per 100 subject years), where for each subject and each TEAE preferred term:

$$\text{Time at risk [subject years]} = (\text{date of first onset of AE} - \text{study drug start date} + 1) / 365.25$$

If, for a subject, no treatment emergent adverse event occurred for the preferred term, then the time at risk will be censored at the minimum of (date of death; drug stop date + 7 days; last contact date).

- For each AE, the incidence rate will therefore be calculated as:

$$\text{Incidence rate [per 100 subject years (pt-yrs)]} = 100 * \text{number of subjects with TEAE} / \text{Total TEAE-specific time at risk [subject years].}$$

Exact 95% confidence intervals (CI) around the observed AE incidence rate will also be provided using exact Poisson regression.

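### Phototoxicity, a compound-specific risk in the protocol, has no adverse-event group in the SAP, so no pooled patient-level count or rate by dose is planned

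*SAP*

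**What the plan says.** Protocol 1.4 states the risk and its source: "Since preclinical data indicate that BI 730357 has phototoxicity potential, patients in this trial will be advised to apply protection measures". The same section bars solarium radiation, UV treatment and phototoxic medication until follow-up ends. The theme recurs in the conduct sections. Exclusion criterion 13 (Protocol 3.3.3) covers patients unwilling to follow the UV rules. Table 4.2.2.1: 1 restricts phototoxic and photoallergic drugs until the end of observation. Protocol 4.2.2.2 says that "patients should avoid prolonged exposure to sunlight and artificial UV-light" throughout the study.

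On reporting, SAP 7.8.1 defers to the protocol for AESIs: "The AESI have been defined in the protocol". The list in Protocol 5.2.6.1.4 is hepatic injury, severe infections, opportunistic and mycobacterial infections, and gastric intolerance or gastritis. The SAP then adds its own groups ("Other user-defined special adverse event grouped term for BI 730357 specified in the following") in Table 7.8.1: 1. The table has five rows, numbered 1 to 5 without a gap, and none concerns light-related reactions.

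The exposure-adjusted rate in SAP 7.4.1 is defined "where for each subject and each TEAE preferred term". SAP 6.1 presents such rates in the AE set classified by dose at onset. A sentence after Table 7.8.1: 1 says that the user-defined categories will follow updates of the Safety SAP.

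**The concern.** The protocol treats phototoxicity as a property of this compound and asks patients to change their behaviour for years because of it. The SAP gives it no summary of its own. Gastritis makes the contrast plain: the protocol does not expect it in humans, yet it is an AESI and has its own customised query.

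If light-related reactions are coded under more than one preferred term, the report would show several small rows and no line counting the patients who had any such reaction. This is a long-term safety trial meant to support registration, and occurrence of TEAEs is its primary endpoint. What is at stake is a direct, pre-specified answer to how many patients on each dose had a light-related reaction, and at what rate.

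**Working it through.** The plan states no figure on this point, so there is none to reproduce. The check sets the risks discussed in Protocol 1.4 against what the two documents plan to report.

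| Risk in Protocol 1.4 | Protocol AESI | Grouped or separate AE summary in SAP 7.8.1 |
|---|---|---|
| Liver injury | yes | yes, one row |
| Infection | yes | yes, three rows |
| Gastric intolerance, gastritis | yes | yes, one row for gastritis |
| MACE | no | yes, adjudicated events |
| Phototoxicity | no | no |
| Hypersensitivity | no | no |

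Malignancy also has no row, but Protocol 5.2.6.1.3 makes new cancers serious in every case, so they reach the serious-AE table.

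**What is planned for a light-related event.** It enters the tables by treatment, system organ class and preferred term. Where applicable it also enters those for drug-related, serious, discontinuation-leading, other significant and worst-intensity AEs. Its preferred term gets an exposure-adjusted rate by dose at onset. No planned output counts patients with at least one event from a defined set of light-related terms.

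**Why term rates do not add up to a group rate.** A term's rate is 100 × patients with the term / patient-years at risk for that term. Two things break the sum:

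- A patient with two terms is counted in both numerators, which pushes the sum up.
- Time at risk stops at the first onset of each term separately. For a group it stops at the first onset of any term, so the group denominator is never larger than a term's denominator. This pushes the sum down.

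**Hypothetical illustration.** The counts, their split and the patient-years are all assumptions. Take 8 patients in one dose column, split 3/2/2/1 over four terms, with the same patient-years (PY) used for every row. The exact Poisson limits for x events are χ²(0.025; 2x)/2 and χ²(0.975; 2x+2)/2, each multiplied by 100/PY.

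| PY | Group, x = 8 | x = 3 | x = 2 (two rows) | x = 1 |
|---|---|---|---|---|
| 90 | 8.89 (3.84–17.51) | 3.33 (0.69–9.74) | 2.22 (0.27–8.03) | 1.11 (0.03–6.19) |
| 200 | 4.0 (1.73–7.88) | 1.5 (0.31–4.38) | 1.0 (0.12–3.61) | 0.5 (0.01–2.79) |
| 400 | 2.0 (0.86–3.94) | 0.75 (0.15–2.19) | 0.5 (0.06–1.81) | 0.25 (0.01–1.39) |

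At 200 PY with eight different patients, 1.5 + 1.0 + 1.0 + 0.5 = 4.0. The sum matches the group rate, and only its interval is missing. If one patient had two of the terms, the rows would still sum to 4.0, but the group rate would be 100 × 7/200 = 3.5. With two such patients it would be 100 × 6/200 = 3.0. The tables alone do not show which case applies.

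**The case against.** The strongest reply is that little is lost. Every preferred term already gets a rate with an exact interval by dose at onset, several cross-cutting tables would show the same events, and SAP 7 lists individual values for all patients. So a reader might infer that phototoxicity gets no incidence and no dose comparison at all, and the documents do not support that. What is missing is the pooled figure. It could be built from the listings, but only with a term list chosen after events labelled by open-label dose have been seen.

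Other points stand in part:

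- Neither document says how light-related reactions would be coded, so their scatter over terms is an assumption. If all fell under one term, the planned row would already be the answer.
- The Safety SAP clause leaves the table open. It permits a new group but promises none, and SAP version 1 is labelled final.
- The Safety SAP and the AE summarisation guideline are not available here, and most of the Drug Profile text is missing. Leaving phototoxicity out may have been a judgement. A reader might infer an oversight, but the documents do not show one.
- A reader might put hypersensitivity on the same footing. Protocol 1.4 raises it only in general terms ("As with all drugs, the potential for hypersensitivity and allergic reactions has to be taken into" consideration), with no preclinical signal and no dedicated restriction. A group for it is a matter of choice.
- A grouped rate would not support a controlled dose comparison. The trial has no randomisation and no hypothesis tests. The 25 and 50 mg doses run for only 12 weeks of this trial, and Part 1 is fasted while Part 2 is fed.

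**Conclusion.** The point holds in a limited form. Phototoxicity is named in the protocol as a compound-specific risk and acted on in conduct, but it is neither an AESI nor a user-defined group. As written, the plan therefore yields no pooled patient-level count or rate for it by dose, and the planned preferred-term rates cannot in general be summed to supply one.

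The size cannot be derived from the documents. It depends on how many events occur, how many terms they use and how many patients have more than one. In the hypothetical 200 patient-year column, the pooled rate behind the same four rows could be 4.0, 3.5 or 3.0 per 100 patient-years. The finding does not affect the primary analysis or any test. It is an optional improvement, at the low end of what should be changed.

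**What to change.** - Add one row to SAP Table 7.8.1: 1 for phototoxicity/photosensitivity, defined by a preferred-term list or customised query fixed before database lock.
- Add one sentence to SAP 7.4.1: for a user-defined group, time at risk runs to the first onset of any TEAE in the group, and patients without one are censored as for a single preferred term.
- Report number, percentage and exposure-adjusted rate with exact 95% CI in the set classified by dose at onset, and number and percentage in the other planned AE sets. Name that set by its description, because SAP 6.1 calls it the fifth while listing four. State that comparison across doses is descriptive.

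A hypersensitivity row is optional.

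The cost is one row, one term list, one sentence and a few more outputs. A table of user-defined AE categories is already planned and the data are already collected. Dosing, restrictions and patient management do not change. The drawback is that a broad query will pick up some unrelated skin events.

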7.8.2 Laboratory data

The analyses of laboratory data will be descriptive in nature and will be based on BI standards [\(6\)](#). The number and percent of patients with possibly clinically significant on treatment abnormalities as identified by use of clinically significant ranges for each laboratory parameter collected will be presented. The patients from both parts of 1407-0030 with possibly clinically significant abnormalities will be identified by actual treatment received at study entry.

Each laboratory value will be graded using the RCTC (version 2.0) grading of laboratory abnormalities. A summary table of the baseline grade compared with the last available on treatment grade will display the number and percent of each type of transition in grade by laboratory parameter within each treatment period and treatment group. A second table will show the number and percent of patients with each type of transition from baseline to their worst on-treatment grade.

A graphical summary highlighting potential cases of Hy's Law by actual treatment received at study entry will be presented. The maximum on-treatment values of total bilirubin and ALT will be plotted each on a scale as multiples of the upper limit of normal. The figure will show areas that meet the criteria of cholestasis (total bilirubin $> 2 \times$ ULN), Temple's corollary (ALT $> 3 \times$ ULN) and Hy's Law as the combination of these two factors. A similar figure using maximum AST values in place of ALT will be constructed. An accompanying listing will show by sample date and study day the full course of the total bilirubin, ALT, AST and alkaline phosphatase values for patients whose total bilirubin are $> 2 \times$ ULN or AST or ALT values $> 3 \times$ ULN at any time during the study (all treatment periods). The listing will indicate where the value meets the criteria, either falling in the cholestasis range, that for Temple's corollary or where the combination meets that for Hy's Law itself.

Laboratory measurements taken up to the residual effect period of 7 days after the last administration of study drug will be considered as on-treatment.

Study visits will be presented by the Visit labels in [Table 6.7:1](#).

